### 7.4.6.1.6 Gastro-Intestinal Toxicities (Diarrhoea, Nausea)

In non-clinical studies in different species (dog, rat, mouse), CB-103 administered at different doses and administration schedules did not show any gastro-intestinal toxicities, e.g. diarrhoea, weight loss. However, as other NOTCH inhibitors (GSIs, mABs) have shown diarrhoea as their major DLT, there might be a risk for CB-103 to also develop gastro-intestinal toxicities. In the event that diarrhoea is observed in clinical trial patients, the following algorithm for CB-103 dose modifications should be followed. Furthermore, Sections 7.4.7.2 to 7.4.7.4 provide a management plan for the occurrence of diarrhoea with a description of measures and treatment suggestions.

**Table 9** Dose modifications for gastro-intestinal toxicities

Dose Modifications for CB-103	
Worst Toxicity CTCAE Grade unless otherwise specified (Value)	At any time during a cycle of CB-103 (including intended day of dosing)
Gastro-intestinal toxicities	
Grade 1	Maintain dose level
Grade 2 (see Sections 7.4.7.2 to 7.4.7.4 for treatment algorithm)	Omit dose administration until recovery to Grade ≤ 1 or baseline then continue at current dose level if grade 2 toxicity persisted for ≤ than 7 days. If grade 2 toxicity persisted for more than 7 days decrease dose by 1 dose level after resolution to Grade 0 or baseline
Grade 3 (see Section 7.4.7.2 to 7.4.7.4 for treatment algorithm)	Omit dose administration until recovery to Grade ≤ 1 or baseline then decrease the next scheduled dose by 1 dose level
Grade 4 (see Section 7.4.7.2 to 7.4.7.4 for treatment algorithm)	Omit dose administration until recovery to Grade ≤ 1 or baseline then decrease the next scheduled dose by 1 dose level In the event Grade 4 toxicity lasts > 24 hours despite maximal medical attention discontinue treatment. If grade 4 toxicity lasts < 24 hours reduce dose by 1 dose level at next cycle If toxicity recurs discontinue treatment.
All grades	At the first sign of abdominal cramping, loose stools, or onset of diarrhoea, the patient should be treated according to Sections 7.4.7.2 to 7.4.7.4 according to the recommended treatment algorithm. Omit dose administration of CB-103 for ≥ CTCAE grade 2 diarrhoea only if diarrhoea could not be controlled despite the use of optimal anti-diarrhoea treatments.

 Common Terminology Criteria for Adverse Events (CTCAE Version 4.03)

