If a patient concurrently experiences both haematological and non-haematological toxicities, then dose modifications for CB-103 should follow the most conservative approach, as outlined in Section [7.4.6.1.1](#), depending on the specific hematologic and non-hematologic toxicities.

Patients who discontinue from the study for a treatment-related adverse event or an abnormal laboratory value, must be followed up until fully recovered, according to the judgement of the Investigator.

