### **7.4.6.1 Follow-up Evaluations and Dosing Modifications for Toxicities**

The follow-up evaluations for toxicities apply during or beyond cycle 1 in Part A, and throughout Part B of the study.

The following sections outline the specific dose modifications for CB-103 for haematologic and non-haematologic toxicities and should be followed by the Investigator accordingly.

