#### **12-24 hours later:**

##### **Diarrhoea resolved**

- Continue instructions for dietary modification
- Gradually add solid foods to diet
- Discontinue loperamide after 12-hours diarrhoea-free interval

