#### After 12-24 hours:

- If diarrhoea persisting administer high dose corticosteroids and consider subcutaneous (s.c.) Sandostatin/octreotide (100-500 µg three times daily [TID])
- Continue i.v. fluids, parenteral nutrition and antibiotics as needed
- If diarrhoea grade 3 or 4 still persists patients should receive besides corticosteroids opium tincture or dihydrocodeine tartrate injections s.c. or intramuscular (i.m.)
- If diarrhoea grade 3 or 4 is still persisting s.c. Sandostatin/octreotide (500-1000 µg TID) should be administered.
- To control and/or resolve diarrhoea, next cycle of treatment should be delayed by 1 or 2 weeks. Treatment should be continued only when diarrhoea resolved.

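### Table 9 gives opposite instructions on holding CB-103 for grade 2 diarrhoea that responds to treatment, and no text says which row prevails

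*Protocol*

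**What the plan says.** Protocol Section 7.4.6.1.6 introduces Table 9 with the words "In the event that diarrhoea is observed in clinical trial patients, the following algorithm for CB-103 dose modifications should be followed". The table is therefore the diarrhoea rule, although its title covers gastro-intestinal toxicity in general.

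- The Grade 2, 3 and 4 rows each begin "Omit dose administration until recovery to Grade" 1 or lower, or baseline. They then differ on the dose at restart. Each also points to the diarrhoea treatment sections, 7.4.7.2 to 7.4.7.4.
- The All grades row sends the patient to the same treatment sections at the first sign of symptoms. It then says to omit CB-103 for grade 2 or higher "diarrhoea only if diarrhoea could not be controlled despite the use of optimal anti-diarrhoea treatments".

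Section 7.4.6.1 states that the follow-up evaluations for toxicities "apply during or beyond cycle 1 in Part A, and throughout Part B of the study". Section 7.4.7.3 treats grade 1 or 2 diarrhoea with loperamide and reassesses "12-24 hours later". For grade 3 or 4, Section 7.4.7.4 says that the "next cycle of treatment should be delayed by 1 or 2 weeks" and adds: "Treatment should be continued only when diarrhoea resolved".

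**The concern.** A patient has grade 2 diarrhoea that comes under control with loperamide. A site reading the Grade 2 row stops CB-103 at onset. A site reading the All grades row keeps dosing. Both can say they followed the protocol, and no site can follow both rows.

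This is a safety dosing rule for a foreseeable event. The same section notes that diarrhoea was the major DLT of other NOTCH inhibitors, and Section 2.5.6 reports related diarrhoea in 20% of the first 41 patients. Sponsor approval of dose adjustments (Section 7.4.5) is required only in Cycle 1 of Part A. SAP 5.7.1 tabulates adverse events leading to interruption, and SAP 5.5 reports compliance as actual over planned dose. The same episode can therefore count as an interruption at one site and not at another.

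**Working it through.** The plan gives no figure on this point. The check compares the rows, looks for a tie-breaker, and then sizes the gap.

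**1. The rows side by side, for diarrhoea**

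| Situation | Grade row | All grades row |
|---|---|---|
| Grade 2, responds to treatment | Hold from onset until grade 1 or lower or baseline | Do not hold |
| Grade 2, not controlled | Hold | Hold |
| Grade 3 or 4, responds to treatment | Hold, then reduce one level (grade 4 beyond 24 hours: discontinue) | Do not hold |
| Grade 3 or 4, not controlled | As above | Hold |

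The rows disagree in the first and third lines. The All grades row speaks only to the hold; it does not contradict the dose reductions.

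**2. Search for a tie-breaker**

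- Section 7.4.5, worst toxicity: applies when there are several toxicities, not when two rows cover one event.
- Section 7.4.5, "dose modifications for CB-103 should follow the most conservative approach": limited to concurrent haematological and non-haematological toxicity.
- Section 7.4.5, investigator decision: covers reductions and resumption, not which row governs the hold.
- Section 7.4.7.3: gives anti-diarrhoeal treatment and is silent on CB-103.
- Section 7.4.7.4: leans towards holding, but only for grade 3 or 4.
- SAP 2.1.4: refers back to protocol 7.4.5.

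None settles the grade 2 case.

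**3. Size per episode**

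Inputs: once-daily dosing and 28-day cycles (Section 7.4); first reassessment at 12 to 24 hours (Section 7.4.7.3). Once the diarrhoea is at grade 1 or lower, both rows allow dosing, so the dispute lasts only from onset to recovery.

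- Doses in dispute = hours to recovery / 24. At 12 hours, 12/24 = 0.5; at 24 hours, 24/24 = 1. That is about one dose.
- Share of a cycle: 1/28 = 3.6%.

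**4. Effect on DLT and DDS status**

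- Both the missed-dose DLT criterion (synopsis) and the DDS exposure criterion (Section 10.1) turn on 21 of 28 days. Omitted days tolerated: 28 − 21 = 7, or 7/28 = 25%.
- At about one dose per episode, it would take 8 separate treatment-responsive episodes in Cycle 1 to exceed 7.
- Grade 2 diarrhoea is not itself a DLT; the synopsis requires grade 3 or higher for at least 72 hours despite treatment.

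**The case against.** The strongest reply is that the rows can be read together. The grade rows cover all gastro-intestinal toxicity, while the last row names only diarrhoea and uses limiting language. On that reading, a site treats diarrhoea first and goes to the grade row only if treatment fails. The lead-in is compatible with this, because the last row is part of the same algorithm.

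This is a sensible reading and probably the intended one. It does not settle the matter, for three reasons. No text states it. The grade rows are diarrhoea rules in their own right, since they cite the diarrhoea sections. And taken literally it would lift the hold for controlled grade 3 and 4 diarrhoea as well, against those rows and against the direction of Section 7.4.7.4. A site relying on the exception has to guess where it stops. Table 9 also does not define control or say when to judge it.

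The reply is right that little depends on this. In an open-label, uncontrolled study, the rows differ only over a short window.

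**Conclusion.** The inconsistency is real and worth correcting, but minor. It puts about one once-daily dose per treatment-responsive grade 2 episode in dispute, on the assumption that such an episode recovers by the 24-hour check. The effect on DLT or DDS status is negligible.

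A reader might infer more than the documents support:

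- *Up to three doses per episode.* Adding the later 2 x 24 hour step in Section 7.4.7.3 gives 24 + 48 = 72 hours, or three doses (3/28 = 10.7%). But diarrhoea that persists through that step on high-dose loperamide, opiates and corticosteroids leads to hospital admission. It has not been controlled, and both rows then lead to omission.
- *A projected number of affected patients.* Section 2.5.6 gives related diarrhoea at any grade, with no count by grade. Any projection would rest on an assumed grade mix and would be too wide to inform.
- *A second conflict over restart.* Section 7.4.7.4 concerns delay of the next cycle at grade 3 or 4. Other dose-modification tables use resolution to mean grade 1 or lower, and Table 9 itself asks for grade 0 or baseline after more than 7 days at grade 2. The wording does not establish a separate contradiction.
- *A threat to the maximum tolerated dose.* The 7-day allowance in Cycle 1 rules this out in practice.

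**What to change.** Add one precedence sentence to Table 9 with a single decision time, for example: *For grade 2 diarrhoea, start treatment per Section 7.4.7.3 and omit CB-103 only if it has not recovered to grade 1 or lower or baseline by the 24-hour check; the grade 3 and 4 rows always apply.* The decision time is the outer edge of the reassessment window already in 7.4.7.3, so no new visit or test is needed. A single time matters: with two permitted times, sites could still differ.

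The cost is one sentence in a protocol amendment. No endpoint, sample size or analysis changes. The sentence does narrow the stated exception from grade 2 or higher to grade 2 only, giving a few more omitted doses than the permissive reading. That is a dosing decision for the sponsor to take explicitly.

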### 7.4.6.1.7 Non-Laboratory Toxicities

Patients who experience non-laboratory toxicities related to CB-103 must be evaluated at least once a week following demonstration of the toxicity until resolution of the toxicity to allow for re-treatment, stabilisation of the toxicity, or study treatment completion.

**Table 10** Dose modifications for non-laboratory toxicities

Dose Modifications for CB-103 post cycle 1	
Worst Toxicity CTCAE Grade  unless otherwise specified (Value)	At any time during a cycle of CB-103 (including intended day of dosing)
Non-laboratory adverse events	
Grade 1 or 2	Maintain dose level
Grade 3	Omit dose administration until resolved to $\leq$ grade 1, then $\downarrow$ 1 dose level
Grade 4	Omit dose administration and discontinue patient from study

 Common Terminology Criteria for Adverse Events (CTCAE Version 4.03)

### 7.4.7 Diarrhoea and Nausea Management Plan

Although no signs of gastro-intestinal toxicities (e.g., diarrhoea) were observed in the non-clinical safety and toxicology studies in different species (dog, rat, mouse) treated with CB-103 at different doses and administration schedules, the occurrence of diarrhoea cannot be excluded.

There is **no a priori prophylaxis** for nausea, vomiting, and/or diarrhoea. Any of these symptoms constitute DLT only if they reach Grade  $\geq$ 3 severity in Cycle 1 despite the following adequate supportive care measures:

- Nausea and/or emesis:
  - Metoclopramide +/- meclozine
  - Dexamethasone 2 mg p.o. in case of Grade 3 nausea/emesis
- Diarrhoea:
  - Loperamide 4 mg p.o. as needed

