## DOSE-LIMITING TOXICITY (DLT)

DLT is defined as an adverse event or abnormal laboratory value assessed as unrelated to disease progression, inter-current illness, or concomitant medications, that occurs  $\leq$  28 days following the first dose of CB-103 (Cycle 1) and that meets any of the following criteria shown in the table below.

**Note:** For T-ALL/T-LBL patients enrolled into the confirmatory cohort of Part A or expansion cohort of Part B of the study, haematological toxicity in non-responding patients, or death after progression should not be considered as DLT.

Toxicity	Any of the following criteria
Haematology	$\geq$ CTCAE grade 3 neutropenia (ANC $<$ $1.0 \times 10^9/L$ ) lasting for $\geq$ 7 days 
	$\geq$ CTCAE grade 4 neutropenia (ANC $<$ $0.5 \times 10^9/L$ ) 
	Febrile neutropenia (ANC $<$ $1.0 \times 10^9/L$ , fever $\geq$ $38.3^\circ C$ ) 
	CTCAE grade 3 thrombocytopenia (platelets $<$ $50-25 \times 10^9/L$ ) lasting for $\geq$ 7 days and/or with signs of bleeding 
	CTCAE grade 4 thrombocytopenia (platelets $<$ $25 \times 10^9/L$ ) 
	$\geq$ CTCAE grade 4 anaemia 
Cardiac	$\geq$ CTCAE grade 3
	$\geq$ CTCAE grade 3 hypertension for $>$ 14 consecutive days despite optimal anti-hypertension therapy
Renal	Serum creatinine $>$ 2 x ULN
Hepatic	$\geq$ CTCAE grade 3 total bilirubin ( $>$ 3 x ULN)
	CTCAE grade 2 total bilirubin lasting for $\geq$ 7 days.
	$\geq$ CTCAE grade 2 total bilirubin and $\geq$ CTCAE grade 2 ALT or AST
	CTCAE grade 3 ALT or AST lasting for $\geq$ 7 days
	CTCAE grade 4 ALT or AST
	Hepatic lab parameters fulfilling Hy's Law: AST/ALT 3 x ULN and concomitant 2 x ULN for bilirubin 
Pancreatic	$\geq$ CTCAE grade 3 pancreatitis
	CTCAE grade 3 asymptomatic serum lipase lasting for $\geq$ 7 days
	CTCAE grade 3 symptomatic serum lipase
	CTCAE grade 4 serum lipase
Other adverse events	Any CTCAE grade 5 toxicity
	$\geq$ CTCAE grade 3 blurred vision or any other eye disorder
	$\geq$ CTCAE grade 3 vomiting or nausea for $\geq$ 72 hours despite optimal anti-emetic therapy 
	$\geq$ CTCAE grade 3 diarrhoea for $\geq$ 72 hours despite optimal anti-diarrhoea treatment 

CONFIDENTIAL

May not be used, divulged, published, or otherwise disclosed without the consent of Cellestia Biotech AG

	Any other ≥ CTCAE grade 3 adverse event, except for the exclusions noted below

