	Inability to administer CB-103 on ≥ 75% of scheduled treatment days during cycle 1 (i.e., ≥ 21 days for a 28-day daily dosing schedule) due to unresolved adverse event of any grade related to CB-103.
	Delay in 2 nd cycle administration due to failure of recovery from a possibly, probably or definitely related adverse event to grade ≤ 1 or baseline by Day 43 (D28 of cycle 1 + 15 days), except for alopecia.
Exceptions to DLT criteria	CTCAE grade 3 or 4 elevations in alkaline phosphatase
	< 96 hours of CTCAE grade 3 fatigue
	Investigations (e.g., laboratory values) CTCAE grade ≥ 3 which are judged not clinically significant by the Investigator 

Abbreviations: ALT, alanine aminotransferase; ANC, absolute neutrophil count; AST, aspartate aminotransferase; CTCAE, Common Terminology Criteria for Adverse Events; DLT, dose-limiting toxicity; PRBC, packed red blood cells; ULN, upper limit of normal.

NCI CTCAE v4.03 will be used for all grading.

 Patients may receive supportive care (e.g. use of granulocyte-colony stimulating factor [G-CSF], packed red blood cells (PRBCs), platelets) as per local institutional guidelines. However, during the DLT period it is not allowed to administer these supportive measures prophylactically.

 Patients fulfilling the criteria for Hy's law will need to be immediately discontinued from treatment

 Optimal therapy for vomiting or diarrhoea will be based on institutional guidelines and based on Section 7.4.7, with consideration of the prohibited medications listed in the protocol.

 An abnormal lab value / investigation should be deemed clinically significant (assessed by the Investigator) if either of the following conditions is met:

- The abnormality suggests a disease and/or organ toxicity that is new or has worsened from baseline
- The abnormality is of a degree that requires additional active management, e.g., change of dose, discontinuation of the drug, close observation, more frequent follow-up assessments, or further diagnostic investigation.

Therefore, a clinically significant lab value is one that indicates a new disease process, an exacerbation or worsening of an existing condition, or requires further action(s) to be taken.

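### The DLT table has no duration-free grade 4 criterion for vomiting or diarrhoea, so some short life-threatening events would count as no DLT; section 7.4.7 also drops the 72 hours

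*Protocol*

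**What the plan says.** Protocol 7.4.4 sends the reader to the DLT table in the synopsis for the criteria. In that table, grade 3 or higher nausea or vomiting counts if it lasts at least "72 hours despite optimal anti-emetic therapy", and grade 3 or higher diarrhoea if it lasts at least "72 hours despite optimal anti-diarrhoea treatment".

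Other rows pair a time-limited grade 3 criterion with a grade 4 criterion that has no time limit. Examples are "CTCAE grade 4 serum lipase" and "CTCAE grade 4 ALT or AST"; neutropenia and thrombocytopenia follow the same pattern.

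Two general rows also bear on the point:

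- A catch-all row takes in any other event at or above a "grade 3 adverse event, except for the exclusions noted below". The listed exclusions are alkaline phosphatase elevations, grade 3 fatigue under 96 hours, and investigations judged not clinically significant. No gastrointestinal event is listed.
- A dosing row counts inability to give CB-103 on at least 75% of Cycle 1 days (21 of 28) "due to unresolved adverse event of any grade related to CB-103".

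Footnote 3 says optimal therapy for vomiting or diarrhoea is "based on institutional guidelines and based on Section 7.4.7". Section 7.4.7 then states its own DLT condition: "Any of these symptoms constitute DLT only if they reach Grade" 3 or above in Cycle 1 despite the listed supportive care. It gives no number of hours.

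Table 9 (7.4.6.1.6) stops treatment for grade 4 gastrointestinal toxicity lasting over 24 hours and reduces the dose if it lasts less. Table 11 defines grade 4 vomiting and diarrhoea as life-threatening and has no grade 4 for nausea.

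**The concern.** DLTs in Cycle 1 are the primary endpoint of the escalation and the only outcome the Bayesian logistic regression model (BLRM) uses. Two things can go wrong.

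- **Under-counting.** A life-threatening vomiting or diarrhoea event that responds within 72 hours can fall outside every DLT row, while a grade 4 lipase or transaminase value of any duration counts.
- **Over-counting.** Footnote 3 takes a site to 7.4.7 to judge optimal therapy. The site meets a DLT sentence there without the 72 hours and may call a shorter grade 3 event a DLT.

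The symptoms are not remote. Protocol 2.5.6 lists nausea (24%) and diarrhoea (20%) as the commonest related treatment-emergent events, and 7.4.6.1.6 calls diarrhoea the major DLT of other NOTCH inhibitors.

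**Working it through.** **1. Which grade 4 events escape.** Take vomiting or diarrhoea in Cycle 1, related to CB-103.

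| Grade 4 event | Table 9 action | 72-hour row | 75%-of-doses row | DLT? |
|---|---|---|---|---|
| Under 24 h | interrupt, then one dose level lower | not met | not met if 21+ days dosed | no |
| 24 to 72 h, stopped before 21 days of dosing | discontinue | not met | most naturally met | yes |
| 24 to 72 h, after 21+ days of dosing | discontinue | not met | not met | no |
| 72 h or more | discontinue | met | not needed | yes |

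The catch-all row does not clearly close the gap. If *any other* means events without their own row, it skips vomiting and diarrhoea. If it includes them, it also catches every grade 3 event under 72 hours, because none is excluded, and the 72-hour condition then does nothing. The first reading is the natural one.

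Protocol 10.1 admits a patient without a DLT to the dose-determining set (DDS) after at least 21 days at the planned dose, 28 days of observation and the required safety evaluations. A patient in the first or third line who meets these enters the model as having no DLT. Replacement under 8.11.1.1 would add a patient; it would not turn the event into a DLT.

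**2. What one changed call does.** Inputs are from 10.5.1.2, 10.5.1.3 and Table 19:

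- Model: logit p(d) = log α + β·log(d/150).
- Prior on (log α, log β): equal mixture of normals with means (−1.122, 0.299) and (−1.682, −0.101), SDs 1.985 and 0.991, correlation about 0.
- Posterior ∝ prior × ∏ p(d)^x (1 − p(d))^(n−x), for x DLTs in n patients at each dose, evaluated on a grid.
- P(overdose) = P(p ≥ 0.33). A dose is barred above 0.25.

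Check against the plan's own P(overdose) figures (Table 20 and Appendix 10 Table 1):

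| Case | Recomputed | Stated |
|---|---|---|
| Prior, 120 mg | 0.297 | 0.298 |
| Scenario 1, 30 mg | 0.029 | 0.031 |
| Scenario 2, 15 mg | 0.241 | 0.239 |
| Scenario 4, 60 mg | 0.032 | 0.035 |
| Scenario 5, 30 mg | 0.110 | 0.121 |
| Scenario 7, 60 mg | 0.157 | 0.162 |

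The largest difference is 0.011. After 0/3 at 15 mg, P(overdose) at 60 mg is:

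| DLTs at 30 mg | P(overdose) at 60 mg | 60 mg |
|---|---|---|
| 0/3 | 0.032 | open |
| 1/3 | 0.282 | barred |
| 1/4 | 0.230 | open |
| 1/5 | 0.189 | open |
| 1/6 | 0.157 | open |

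Appendix 10 agrees where it overlaps: its next dose is 60 mg in scenarios 4 and 7 and stays at 30 mg in scenario 5.

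**3. Whether anything has happened yet.** Protocol 2.5.6 gives the adverse events to 20 August 2020 as 73.3% grade 1, 21% grade 2 and 5.7% grade 3. These sum to 100.0%, which leaves no grade 4 event. One unrelated fatal event in the same section is not visible in that split. The single DLT reported is a GGT elevation, not a gastrointestinal event.

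**The case against.** The strongest reply is that this is editorial. Section 7.4.4 makes the table the source, footnote 3 cites 7.4.7 only for what counts as optimal therapy, and *only if* states a necessary condition. That stands for 7.4.7: a reader might infer a second, competing DLT rule, and the documents do not support it.

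A reader might also infer that a patient stopped early for grade 4 diarrhoea is replaced and the event never reaches the model. That is not supported either. Table 9 stops treatment because the event has persisted over 24 hours despite maximal care, so it is unresolved when dosing ends. The shortfall below 21 days then most naturally meets the 75%-of-doses row. Section 8.11.1.1 does not replace a patient who stops for a DLT.

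Other controls also stand. Grade 4 events are reported as serious (9.3.3). The Cohort Review Committee weighs non-DLT events before each dose decision (10.5.1.2). Related grade 2 or higher toxicity in more than one patient limits the next increase to 50% (7.4.3). These reduce the consequence, but they do not put the event into the DLT count.

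Finally, the 30 and 60 mg once-daily levels are long passed. This is correct: the figures show how sensitive a small cohort is, and they do not measure harm done.

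**Conclusion.** The concern holds as a minor point. The gap is narrow: grade 4 vomiting or diarrhoea under 24 hours handled by dose reduction, or of 24 to 72 hours after 21 or more days of dosing. Either would enter the DDS as having no DLT if the other requirements of 10.1 are met. The 7.4.7 sentence adds a separate risk of over-calling short grade 3 events.

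This rests on the natural readings of the catch-all row and of *unresolved* in the 75%-of-doses row. One changed call can reverse a decision in a cohort of 3, but not in the 4-to-6-patient cases computed.

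It would be wrong to infer that past escalation was distorted. No misclassified event is shown, and the grade split leaves no grade 4 event to reclassify as of August 2020. The risk lies in cohorts still being evaluated, such as the twice-daily schedule. Its effect there cannot be computed, because the mixture weights of that model's prior are not given.

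**What to change.** Make three changes:

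1. In the DLT table, add: *CTCAE grade 4 vomiting or diarrhoea of any duration*. Nausea is left out because Table 11 has no grade 4 for it.
2. In the exceptions row, add: *CTCAE grade 3 nausea, vomiting or diarrhoea lasting < 72 hours with optimal supportive care*. This settles the catch-all row for grade 3.
3. In 7.4.7, replace the DLT sentence with: *The DLT criteria for nausea, vomiting and diarrhoea are those in the synopsis DLT table; the measures below are the supportive-care standard for applying them.*

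No new data or patients are needed. The cost is procedural: the first change alters the definition of the escalation primary endpoint, so under 13.5.1 it belongs in a substantial amendment with ethics and authority approval.
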